#### **10.1.4. Population-Level Summary**

The population-level summary for the primary endpoint is the difference in primary variable means between each AGN-241751 dose and placebo.

Similarly, the population-level summary for the secondary endpoint is the difference in secondary variable means between each AGN-241751 dose and placebo.

### **10.2. Sample Size Determination**

The sample size of approximately 50 randomized participants in each of the 5 treatment groups is not based on statistical power consideration due to the lack of information of AGN-241751 for the variability of change from baseline to 1 day after first dose in MADRS total score.

### **10.3. Populations for Analyses**

The analysis populations will consist of participants as defined below:

- The modified intent-to-treat (mITT) population includes all randomized participants who received at least 1 administration of study treatment, and have a baseline MADRS total score and at least 1 postbaseline assessment for the MADRS total score during the double-blind treatment period. Participants will be summarized according to the randomized study treatment.
- The safety population includes all participants who received  $\geq 1$  administration of study treatment. Participants will be summarized according to the study treatment they actually received.

### **10.4. Statistical Analyses**

The study statistical analysis plan (SAP) will be developed and finalized before database lock and will describe in detail the participant populations to be included in the analyses, the safety and efficacy analysis, and the procedures for accounting for missing or unscheduled data. This section is a summary of the planned statistical analyses of the primary and secondary endpoints.

#### **10.4.1. Efficacy Analyses**

The efficacy analyses will be based on the mITT population. Baseline for efficacy is defined as the last nonmissing efficacy assessment before the first dose of study treatment. All statistical tests will be 2-sided hypothesis tests performed at the 5% level of significance for main effects. All confidence intervals will be 2-sided 95% confidence intervals, unless stated otherwise.

For efficacy analyses in which study center is a factor, a small center will be defined as a center with fewer than 2 participants in the mITT Population. All the small centers will be pooled to form a pseudo-center. If the pseudo-center is still a small center, it will be pooled with the smallest non-small center. If there is more than one smallest non-small center, the small pseudo-center will be pooled with the smallest non-small center that has the largest center number.

#### 10.4.1.1. Primary and Secondary Endpoint

To perform the analysis based on the estimands framework, the primary and secondary efficacy endpoints are listed below and analyses will be defined in the following sections. All analyses for other efficacy endpoints listed below will be defined in the SAP.

Primary efficacy endpoint:

- Change from baseline in MADRS total score at 1 day after first dose

Secondary efficacy endpoint:

- Change from baseline in MADRS total score at Week 3

#### 10.4.1.2. Primary and Secondary Analyses

The primary analysis for the primary and secondary endpoints will be performed using a MMRM with treatment group, visit, pooled study center, and treatment group-by-visit interaction as fixed effects and the baseline value and baseline value-by-visit as covariates. An unstructured covariance matrix will be used to model the covariance of within-participant scores. If the model fails to converge based on the unstructured covariance matrix, then structures of Heterogenous Toeplitz, Toeplitz, and Compound Symmetry will be applied, in the specified order, until the model converges. The Kenward-Roger approximation will be used to estimate denominator degrees of freedom (Kenward and Roger 1997). These analyses will be performed based on all postbaseline scores using only the OCs without imputation of missing values.

[figure not shown]
In addition, a sensitivity analysis using the multiple imputation (MI) approach under missing not at random (MNAR) assumptions will be performed on the primary and secondary efficacy parameters.

Detailed methods and procedures for the above outlined missing data-derived sensitivity analyses will be documented in the final SAP prior to the study database lock.

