#### 4. Objectives and Endpoints

The primary objective is to evaluate the efficacy, as measured by improvement in MADRS total score, at 1 day post initial oral dose of AGN-241751 compared with placebo in participants with MDD. The key secondary objective is to evaluate the efficacy at Week 3 of AGN-241751 administered orally once a week compared with placebo in participants with MDD.

Objectives	Endpoints
Primary	

 
To evaluate the efficacy at 1 day post initial oral dose of AGN-241751 compared with placebo in participants with MDD
 
	
 
Change from baseline in MADRS total score at 1 day after first dose
 

Key Secondary	

 
To evaluate the efficacy at Week 3 of AGN-241751 administered orally once a week compared with placebo in participants with MDD
 
	
 
Change from baseline in MADRS total score at Week 3
 

Additional	

 
Additional endpoints to be explored to determine differences between AGN-241751 vs. placebo
 
	
 
Change from baseline in MADRS total score at 4 hours post dose, and on Study Days 5, 8, 9, 12, and 15
 
Change from baseline in Clinical Global Impressions-Severity (CGI-S) at 4 hours post dose, and on Study Days 2, 5, 8, 9, 12, 15, and 22
 
Rate of sustained responders during treatment
 
Rate of responders at 4 hours post dose, and on Study Days 2, 5, 8, 9, 12, 15, and 22
 
Rate of sustained remitters during treatment
 
Rate of remitters at 4 hours post dose, and on Study Days 2, 5, 8, 9, 12, 15, and 22
 
Time to first response
 
Time to first sustained response
 
Time to first remission
 
Time to first sustained remission
 

Objectives	Endpoints
Safety Measures	

• Adverse event (AE) recording, clinical laboratory measures, vital sign parameters, electrocardiograms (ECGs), and physical examinations

• Measure of psychotomimetic effects: Brief Psychiatric Rating Scale Positive Symptoms subscale (BPRS+)

• Measure of dissociative effects: Clinician Administered Dissociative States Scale (CADSS)

• Measure of suicidality: Columbia-Suicide Severity Rating Scale (C-SSRS)

• Measure of cognition/psychomotor function: Symbol Digit Coding (SDC)

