#### 10.4.1.3. Multiple Comparisons Procedure

Let H11, H21, H31, H41 represent the comparisons of AGN-241751 0.25 mg, 1 mg, 3 mg, and 10 mg, respectively with placebo in regarding to the primary efficacy parameter; and let H12, H22, H32, and H42 represent the comparisons of AGN-241751 0.25 mg, 1 mg, 3 mg, and 10 mg, respectively with placebo in regarding to the key secondary efficacy parameter, the graphical procedure as displayed in Figure 10-1 will be employed to controlled the overall familywise error rate (FWER) at  $\alpha = 0.05$ . The  $\epsilon$  in the figure represents a small positive number less than 0.0001.

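### Minor and conditional: if the unstructured and heterogeneous Toeplitz fits both fail, the MMRM fallback puts one variance on every visit, and the Day 2 and Week 3 standard errors are wrong if variance changes over time

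*Protocol*

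**What the plan says.** Protocol 10.4.1.2 uses one MMRM for the Day 2 primary and the Week 3 key secondary endpoint. The covariance is unstructured. If that fit does not converge, "then structures of Heterogenous Toeplitz, Toeplitz, and Compound Symmetry will be applied, in the specified order, until the model converges". On inference it says only: "The Kenward-Roger approximation will be used to estimate denominator degrees of freedom". No robust standard error is named.

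On the data: "These analyses will be performed based on all postbaseline scores using only the OCs without imputation of missing values". Protocol Section 4 lists the additional endpoint "Change from baseline in MADRS total score at 4 hours post dose, and on Study Days 5, 8, 9, 12, and 15". With Day 2 and Day 22 that makes eight postbaseline visits in the model.

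Protocol 10.4.1 sets the error rate: "All statistical tests will be 2-sided hypothesis tests performed at the 5% level of significance for main effects". Section 10.4.1.3 places both endpoints in a graphical procedure with familywise error 0.05. Section 10.2 explains that the sample size is not power-based because of "lack of information of AGN-241751 for the variability of change from baseline to 1 day after first dose in MADRS total score".

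SAP 10.1 specifies the unstructured matrix and no fallback. SAP Section 4 names Amendment 1 as the latest amendment, whereas the protocol is at Amendment 2. SAP Section 17 lists no changes from the protocol.

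**The concern.** The last two structures on the list assume the same variance four hours after the first dose as three weeks later. Nothing in the documents supports that. Protocol 9.1.1 sets the MADRS look-back after baseline to the time since the last evaluation, so the recall window runs from hours to about a week, and equal variances cannot be taken for granted.

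Kenward-Roger is a small-sample adjustment that takes the fitted structure as correct, so it does not repair a wrong one. When treatment-by-visit is in the model and few data are missing, the treatment estimate at a visit stays close to the difference in that visit's means. Its standard error, however, borrows a variance pooled over all eight visits. If variance rises, the primary test loses power and the key secondary test rejects too often.

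**Working it through.** **Inputs.** From the documents: eight postbaseline visits (Protocol Sections 2 and 4), about 50 per arm in five arms (10.2), two-sided 5% (10.4.1). They state no SD, standard error or power, so there is no figure to reproduce. All SDs below are assumptions, and complete data are assumed. Protocol 10.1.3 expects at most 5% to miss treatment at Week 2 or 3.

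**Covariance parameters for eight visits.** Unstructured 8 × 9 / 2 = 36; heterogeneous Toeplitz 8 + 7 = 15; Toeplitz 1 + 7 = 8; compound symmetry 2. Only the first two have a variance for each visit.

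**Formulas.** Let σ_t be the SD at visit t.
- True SE of a dose-placebo contrast = √(2σ_t² / 50).
- Under compound symmetry the model uses the mean of the eight visit variances, so SE ratio (model / true) = pooled SD / σ_t.
- Actual two-sided error = 2[1 − Φ(1.96 × ratio)].

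**One profile in full.** Assumed SDs 5.5, 6.5, 7.5, 8.5, 8.5, 9, 9.5, 10 from 4 hours to Day 22.
- Squares sum to 544.5; 544.5 / 8 = 68.06; pooled SD 8.25; model SE √(2 × 68.06 / 50) = 1.65 at every visit.
- Day 2: true SE √(2 × 42.25 / 50) = 1.30; ratio 1.27; error 2[1 − Φ(2.488)] = 1.3%.
- Day 22: true SE √(2 × 100 / 50) = 2.00; ratio 0.825; error 2[1 − Φ(1.617)] = 10.6%.

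Simulation with correlation decaying over time agrees: 1.3% and 11.6% in 4,000 trials, and 1.4% and 10.5% in a separate run of 20,000. Visit-specific variances in the latter gave 4.8% and 5.2%.

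**Range of assumptions, compound symmetry.**

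| Profile | Assumed SDs, 4 h to Day 22 | Pooled SD | Day 2 ratio; error | Week 3 ratio; error |
|---|---|---|---|---|
| Equal | 8 throughout | 8.00 | 1.00; 5.0% | 1.00; 5.0% |
| Mild rise | 6.61, 7, 7.67, 8.01, 8.1, 8.31, 8.47, 8.75 | 7.90 | 1.13; 2.7% | 0.90; 7.7% |
| Moderate rise | 6.22, 7, 8.34, 9.02, 9.2, 9.62, 9.94, 10.5 | 8.84 | 1.26; 1.3% | 0.84; 9.9% |
| Steep rise | 4.66, 6, 8.29, 9.47, 9.76, 10.48, 11.04, 12 | 9.27 | 1.54; 0.3% | 0.77; 13.0% |
| Falling | 9.67, 9, 7.85, 7.27, 7.12, 6.76, 6.48, 6 | 7.61 | 0.85; 9.8% | 1.27; 1.3% |

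The large-sample limit of homogeneous Toeplitz is close: 2.7 to 2.8% and 7.7 to 7.9% for the mild rise, 1.4% and 10.0 to 10.2% for the moderate rise.

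**Power at Day 2, illustration only.** For an assumed standardised effect of 0.5, the noncentrality is 0.5 / √(2/50) = 2.5. Power is Φ(2.5 − 1.96) = 70.5% with the right SE. At ratio 1.262 it is Φ(2.5 − 2.473), about 51%.

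**Heterogeneous Toeplitz.** With exchangeable true correlation its ratio is 1.00 at both visits under every profile. It does, however, treat unequal gaps as equal lags: 20 hours from the 4-hour visit to Day 2 (24 − 4) and 7 days from Day 15 to Day 22. Under an extreme time-decay correlation (assumed 0.7 per week, no measurement error) the ratios are 0.90 at Day 2 and 1.24 at Day 22, giving errors of 7.9% and 1.5%.

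**Sandwich errors.** In 2,000 null trials (5 × 50, eight visits, 20 centers, the SDs of the full example, correct heterogeneous working covariance, no small-sample correction), rejection was 6.3% at Day 2 and 5.9% at Day 22, with Monte Carlo error about 0.5 points.

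**The case against.** The best defence is that this branch will probably never run. With about 250 participants, eight visits and few expected losses, 36 covariance parameters should be estimable, and heterogeneous Toeplitz comes next with only 15. A fixed order also prevents a structure being chosen after seeing results. All of this stands and makes the point minor.

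A reader might draw three stronger conclusions that the documents do not support.
- *Failure of the unstructured fit alone leads to a common variance.* It does not, because heterogeneous Toeplitz is tried first.
- *The standard errors are wrong whenever Toeplitz or compound symmetry is used, always too large at Day 2 and too small at Week 3.* Equal variances give no error in this calculation and falling variances reverse both directions. No SD is given that would settle which applies.
- *The familywise error rises to about 10%.* The figures above are unadjusted per-comparison rates. The weights and gating are in Figure 10-1 of Protocol 10.4.1.3, which was not available here. If Week 3 tests open only after a Day 2 rejection, an over-conservative Day 2 test would itself limit them.

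It is also fair to say that deleting the last two structures is not enough, since heterogeneous Toeplitz shares the equal-lag assumption. The remedy therefore depends on the robust standard error, and that has a small cost of its own.

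**Conclusion.** The point holds as a minor, conditional weakness. It needs two convergence failures and a variance that changes over time. Given both, the Day 2 and Week 3 standard errors are wrong, and Kenward-Roger does not correct them. If variance rises, per-comparison error is about 3% at Day 2 and 7 to 8% at Week 3 for a mild rise, and about 1.3% and 10 to 11% for a moderate one. These sizes rest wholly on assumed SDs and complete data, and the effect on familywise error is not quantified. One part needs no assumption: the current protocol has a fallback rule and SAP 10.1 has none, so the two must be reconciled in any case.

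**What to change.** In Protocol 10.4.1.2:
1. Delete Toeplitz and compound symmetry from the list.
2. For any structure other than unstructured, including heterogeneous Toeplitz, replace Kenward-Roger with empirical (sandwich) standard errors, with a small-sample correction where available.
3. If nothing converges, analyse Day 2 and Week 3 by separate ANCOVAs with treatment, baseline and pooled center. Each uses only its own visit's variance.

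Write the same rule into SAP 10.1 when the SAP is brought up to Amendment 2, before database lock.

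The cost is wording only: no new data, visits or participants. The statistical cost is the slight anticonservatism of uncorrected sandwich errors, about 6% against 5% in the simulation above. The last-resort ANCOVA also leaves out participants with no score at that visit.

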#### 10.4.1.3. Multiple Comparisons Procedure

Let H11, H21, H31, H41 represent the comparisons of AGN-241751 0.25 mg, 1 mg, 3 mg, and 10 mg, respectively with placebo in regarding to the primary efficacy parameter; and let H12, H22, H32, and H42 represent the comparisons of AGN-241751 0.25 mg, 1 mg, 3 mg, and 10 mg, respectively with placebo in regarding to the key secondary efficacy parameter, the graphical procedure as displayed in Figure 10-1 will be employed to controlled the overall familywise error rate (FWER) at  $\alpha = 0.05$ . The  $\epsilon$  in the figure represents a small positive number less than 0.0001.

**Figure 10-1 Graphical Procedure for Primary and Key Secondary Hypotheses**

#### 10.4.2. Safety Analyses

The safety analysis will be performed using the safety population for the double-blind treatment period and for the safety follow-up period, if applicable, and will be fully defined in the SAP. The safety parameters will include AEs, clinical laboratory including potential Hy's law cases, vital signs, ECG, C-SSRS, BPRS+, CADSS, and SDC parameters. For each safety parameter, the last nonmissing safety assessment before the first dose of study intervention will be used as the baseline for all analyses of that safety parameter.

##### 10.4.2.1. Adverse Event

An AE will be considered a treatment-emergent adverse event (TEAE) if:

- The AE began on or after the date of the first dose of study treatment; or
- The AE was present before the date of the first dose of study treatment, but increased in severity or became serious on or after the date of the first dose of study treatment

If more than 1 AE is reported before the first dose of study treatment and is coded to the same preferred term, the AE with the greatest severity will be used as the benchmark for comparison with the AEs that were also coded to that preferred term and that occurred during the period. An AE that occurs more than 30 days after the last dose of study treatment will not be counted as a TEAE.

An AE will be considered a treatment-emergent serious adverse event (TESAE) if it is a TEAE that additionally meets any SAE criteria

The number and percentage of participants reporting TEAEs in each study treatment will be tabulated as follows:

- By system organ class and preferred term
- By system organ class, preferred term, and severity.

The number and percentage of participants reporting treatment related TEAEs in each study treatment will be tabulated by system organ class and preferred term.

If more than 1 AE is coded to the same preferred term for the same participant, the participant will be counted only once for that preferred term using the most severe and most related occurrence for the summarization by severity and by relationship to study treatment.

Summary tables will be provided for participants with TESAEs and participants with TEAEs leading to discontinuation if 2 or more participants reported such events. Listings of all AEs, SAEs, and AEs leading to discontinuation by participant will be presented.

The definitions of an AE and SAE can be found in [Appendix 4](#).

#### **10.4.2.2. Clinical Laboratory Assessments**

Descriptive statistics of actual values and change from baseline for clinical laboratory values (in SI units) will be presented at each assessment timepoint by treatment. In addition, descriptive statistics for values and changes from the baseline values in conventional units at each assessment timepoint will be presented for selected clinical laboratory parameters listed in the SAP.

The criteria for potentially clinically significant (PCS) laboratory values will be detailed in the SAP. The number and percentage of participants who have PCS postbaseline clinical laboratory values will be tabulated by study treatment at each assessment. The percentages will be calculated relative to the number of participants who have available non-PCS baseline values and at least 1 postbaseline assessment. The numerator will be the total number of participants with available non-PCS baseline values and at least 1 PCS postbaseline value. A supportive listing of participants with PCS postbaseline values will be provided.

#### **10.4.2.3. Vital Signs**

Descriptive statistics of actual values and change from baseline for vital signs (systolic and diastolic BP, pulse rate, weight, and temperature) will be presented at each assessment timepoint by treatment.

Vital sign values will be considered to be PCS if they meet both the observed value criterion and the change from baseline value criterion that will be detailed in the SAP. The number and percentage of participants who have PCS postbaseline vital sign values will be tabulated by study treatment for each assessment. The percentages will be calculated relative to the number of participants who have available baseline values and at least 1 postbaseline assessment. The numerator will be the total number of participants with at least 1 PCS postbaseline value. A supportive listing of participants with PCS postbaseline values will be provided.

#### 10.4.2.4. Electrocardiograms

Descriptive statistics of actual values and change from baseline for ECG parameters (ie, heart rate, PR interval, QRS interval, QT interval, and QTc interval) will be presented at each assessment timepoint by treatment.

The number and percentage of participants with PCS postbaseline values will be tabulated by study treatment. The criteria for PCS ECG values will be detailed in the SAP. The percentages will be calculated relative to the number of participants with an available non-PCS baseline value and at least one postbaseline assessment. The numerator will be the total number of participants with an available non-PCS baseline value and at least one PCS postbaseline ECG value. A supportive listing of participants with PCS postbaseline values will be provided and will include the participant number and the baseline and postbaseline values. A listing of all AEs for participants with PCS ECG values will also be provided.

A shift table from baseline to the end of study in the investigator's overall interpretation of the ECG will be presented by treatment group for the following categories: normal; abnormal, not clinically significant; abnormal, clinically significant. A tabular display of participants with postbaseline clinically significant ECG abnormalities according to the investigator's overall interpretation will be provided.

The number and percentage of participants with a change from baseline QTc  $> 30$  msec but not exceeding 60 msec and of participants with an increase  $> 60$  msec will be tabulated by treatment group. A supportive listing that includes the participant identification number, all QTc values (including change from baseline values), and all AEs will be provided for all participants who have postbaseline QTc changes  $> 30$  msec.

#### 10.4.2.5. Other Safety Parameters

Other safety parameters include the BPRS+, CADSS, C-SSRS, and SDC.

Descriptive statistics of actual values and change from baseline for BPRS+ total score will be presented at each assessment timepoint by treatment.

Descriptive statistics of actual values and change from baseline for CADSS total score will be presented at each assessment timepoint by treatment. The CADSS total score is defined as the sum of scores for 23 subjective items.

The number and percentage of participants with suicidal ideation or suicidal behavior as recorded on the C-SSRS will be summarized by treatment. The distribution of responses for most severe suicidal ideation and most severe suicidal behavior during the participant's lifetime, during the double-blind treatment period, and during the safety follow-up period will also be presented by treatment. Supportive listings will be provided and will include the participant number, lifetime history, and postbaseline values. Intensity of suicidal ideation, suicidal behavior type, and lethality of suicidal behavior will also be included in these listings. A listing of all AEs occurring in participants who have suicidal ideation or suicidal behavior will also be provided.

Descriptive statistics will be presented at each assessment timepoint by treatment for the SDC parameters including the number of symbols completed, the rate of completion (number of

symbols completed/time of trial), the number of corrected responses (symbols completed correctly), and the number of errors (symbols completed incorrectly).

